Subjects in the study are those:

- who have at least a 3 month history of 3-14 migraines, with or without aura, as defined by International Classification of Headache Disorders (ICHD) -3 beta (Appendix 1) or treat with a ergot or triptan and received relief.
- who received a diagnosis of migraine before age 50.
- who have used acute headache medication 14 or fewer days per month in the previous 3 months.

STUDY MEDICATION

Subjects will receive Investigational Drug Product MLD10 as follows: 2 MLD10 caplets, oral, twice daily or placebo caplets as follows: 2 placebo caplets, oral, twice daily.

BACKGROUND & STUDY RATIONALE

Magnesium is frequently used in the treatment and prevention of migraine, though there are relatively few clinical trials supporting its efficacy. While there is a sound scientific rationale for magnesium as a migraine preventative, different forms of magnesium differ significantly in their solubility and bioavailability. In addition, there are challenges in measuring bioactive magnesium levels in the body. Consequently, a discussion of the efficacy of magnesium needs to be specific to the formulation of magnesium being studied, its ability to be adequately absorbed, and physiologically active.

Magnesium is recognized to block the N-methyl-D-aspartate ion-dependent channel. Low levels of magnesium increase the sensitivity of the NMDA receptor to glutamate. Glutamate is an excitatory neurotransmitter and is considered central to the development of cortical spreading depression. In addition, glutamate is considered to play an excitatory role in the hyper-vigilant migraine nervous system. Thus, magnesium properly utilized physiologically has significant potential to protect the nervous system from migraine.

PRIMARY OBJECTIVE

To compare the change from baseline to treatment period months 1, 2, and 3 in the number of migraine headache days of subjects treated with MLD10 versus placebo.

SECONDARY OBJECTIVES

To compare change from baseline of subjects treated with MLD10 versus placebo on the following parameters during a 3 month treatment period:

- the number of headache days
- the average headache duration
- pain severity at headache onset
- the use of acute medications
- Migraine Disability Assessment Scale (MIDAS) scores
- Subject Global Impression of Change (SGIC)
- Physician Global Impression of Change (PGIC)

EXPLORATORY OBJECTIVES

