To compare the change from baseline of subjects treating with MLD10 versus placebo on the following parameters during a 3 month treatment period.

- migraine with aura days
- serum ionized magnesium

SAFETY OBJECTIVES

Safety assessments will include monitoring the parameters during the length of the study.

- adverse events
- physical examination
- urine pregnancy tests for all females of childbearing potential

- vital signs including blood pressure, pulse rate, and weight
- Columbia-Suicide Severity Rating Scale (C-SSRS)
- concomitant medications
- clinical chemistry measurements

SUBJECT SELECTION

Approximately 142 subjects will be randomized from the clinic and general population with a history of mild to severe migraine, with or without aura, that meets the International Classification of Headache Disorders (ICHD-3 beta) definition for episodic migraine with a frequency of 3-14 days of migraine (or headache treated with migraine specific medication) per month. Subjects will have a stable history of headaches meeting the above parameters for at least 3 months prior to enrollment. Subjects on migraine preventative medications will be required to be on a stable regimen for 30 days prior to and throughout the study period.

POWER ANALYSIS

A power analysis, using GPower Version 3.1.7, indicated a total sample size of 128 subjects would be needed to detect medium effects ($d = .25$) with 80% power using an analysis of covariance (ANCOVA) test to include fixed effects, main effects, and interactions with alpha being .05. Given an estimated 10% early termination rate, a total estimated sample size of 142 subjects is needed.

INCLUSION CRITERIA

Subjects must meet the following inclusion criteria:

1. male or female, in otherwise good health, 18 to 65 years of age.
2. history of frequent episodic migraine (3-14 migraine days per month) (with or without aura) according to the ICHD-3 beta for at least 3 months.
3. onset of migraine before age 50.
4. stable history of migraine at least 3 months prior to screening.
5. not currently taking a migraine preventive or has been taking preventive for at least 30 days prior to screening and agrees to not start, stop, or change medication and/or dosage during the study period.
6. if female of childbearing potential, has a negative urine pregnancy test at Visits 1-5 and uses, or agrees to use, for the duration of the study, a medically acceptable form of contraception as listed:

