2. Verify Inclusion/Exclusion Criteria. Subjects will meet all the inclusion and none of the exclusion criteria.
3. Obtain demographics (race, ethnicity, sex, date of birth)
4. Obtain medical, medication, and headache history. Data collected will include medical history and diagnoses, age at onset of migraine and other pertinent migraine/headache history, history of acute and prophylactic headache medications within the past 30 days, and history of other recent/concomitant medications.
5. Obtain date of last menstrual cycle and perform urine pregnancy test, if appropriate. Results of the pregnancy test must be negative to continue in study.
6. Perform physical and neurological examinations.
7. Measure vital signs (height, weight, resting heart rate, and blood pressure).
8. Review Baseline Headache Diary. Subjects will be instructed to complete a daily online headache diary. Assessments to be captured are start/stop time, severity, associated symptoms, use of rescue medications, and unusual symptoms.
9. Administer Columbia-Suicide Severity Rating Scale (C-SSRS).
10. Schedule Visit 2.

VISIT 2 - RANDOMIZATION

1. Verify Inclusion/Exclusion Criteria. Subjects must continue to meet all inclusion (including ≥ 3 days of migraine during baseline) and none of the exclusion criteria.
2. Perform urine pregnancy test, if appropriate. Results of the pregnancy test must be negative to continue in study.
3. Measure vital signs (weight, resting heart rate, and blood pressure).
4. Record any changes to concomitant medications.
5. Record any Serious Adverse Events (SAE) since signing the Informed Consent.
6. Review Baseline Headache Diary for completeness and continuing eligibility.
7. Randomize subject
8. Review Month 1 Headache Diary instructions (same instructions as those discussed for Baseline Headache Diary).
9. Dispense Month 1 study medication. Subjects will be instructed how to take study medication, prohibited medications, dosage limitations of study medication, and storage requirements. Subjects will be instructed to return all used/partially

used/unused study medication at next office visit and medications reconciliation will be performed to ensure a compliance of at least 80%. Subjects not complying at an 80% level will be withdrawn, unless otherwise approved by the Sponsor and/or Clinvest. (Estimated to be < 10%)

10. Administer C-SSRS.
11. Administer MIDAS.
12. Collect serum samples for electrolytes, creatinine, and ionized Mg.
13. Schedule Visit 3.

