Table 1. Study Procedures

	Screening	Randomization	Treatment		
	Visit 1 Day 0	Visit 2 Day 29 (+/- 3)	Visit 3 Day 58 (+/- 3)	Visit 4 Day 87 (+/- 3)	Visit 5 Day 116 (+/- 3)
Informed Consent	X				
Physical/Neurological Exam	X				X
Vital Signs	X	X	X	X	X
Verify Inclusion/Exclusion	X	X			
Subject Randomization		X			
Medical History	X				
Migraine History	X				
Medication History	X				
Update Medications		X	X	X	X
Urine Pregnancy Test	X	X	X	X	X
SGIC					X
PGIC					X
Dispense Study Medication		X	X	X	
Drug Accountability			X	X	X
Headache Diary	X	X	X	X	
Review Diary		X	X	X	X
Collect Adverse Events		X	X	X	X
Administer C-SSRS	X	X	X	X	X
Administer MIDAS		X			X
Serum Electrolytes & Creatinine		X	X	X	X
Serum Ionized Mg		X	X	X	X

STUDY MEDICATION RANDOMIZATION

Eligible subjects will be randomized 1:1 to receive magnesium L-lactate dehydrate (243 mg of elemental mg⁺⁺ BID for a total of 486mg daily) or placebo at Visit 2. If at any time during the

study the subject withdrawals from the study, they will be instructed to return all used packaging and unused medication.

Group A

Subjects randomized to MLD10 (Group A) will be dispensed a 28 day supply of magnesium L-lactate dehydrate 10 mEq (121.5 mg of elemental mg⁺⁺ caplets) for daily treatment. A total of 120 caplets will be given each time at Visit 2, 3, and 4. Additional overage will be given to account for the 3 day window. Subjects will be instructed to take two caplets of study medication BID at about the same time each day (i.e. 8AM & 8PM for a total of 486mg's of elemental mg⁺⁺ per day). Subjects will be instructed regarding storage requirements and will be asked to return all used/partially used/unused medication containers at the next office visit.

Group B

Subjects randomized to placebo (Group B) will be dispensed a 28 day supply of matching placebo for daily treatment. A total of 120 caplets will be given each time at Visit 2, 3, and 4. Additional overage will be given to account for the 3 day window. Subjects will be instructed to take two caplets of study medication BID at about the same time each day (i.e. 8AM & 8PM). Subjects will be instructed regarding storage requirements and will be asked to return all used/partially used/unused medication containers at the next office visit.

RESCUE MEDICATION

Subjects will be instructed they may take their investigator approved rescue medications for headaches, if needed. Rescue medication usage and dosage will be recorded on the headache diary.

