Comprehensive training will be provided by Clinvest to site personnel. Training topics will include protocol, study design, study documents, electronic data capture system, reporting of AEs and pregnancy, and any other study related tasks.

SAFETY MEASURES

Adverse Events

Adverse events (AEs) will be monitored throughout the study. All reported AEs will be documented on the appropriate eCRF.

Physical Examination

At screening and study exit, the investigator will examine the patient for any detectable abnormalities of the following body systems: general appearance; neck (including thyroid); head, eyes, ears, nose, and throat; lungs; heart/cardiovascular; abdomen; neurologic; extremities; back; musculoskeletal; lymphatic; skin; and other. The neurologic examination should be conducted to detect the presence of any significant sensory/motor abnormalities. A digital rectal examination is not required. Gynecological examinations are not required.

Weight should be measured at screening, day 1, and each subsequent office visit using the same scale for all patients at a given investigator site when possible.

Pregnancy tests for all females of childbearing potential. Urine pregnancy testing will be conducted at screening, on day 1, and each subsequent office visit to confirm continued non-pregnant status prior to study drug administration or study completion.

Clinical Laboratory Tests

Blood samples will be collected for clinical laboratory testing at Visits 2-5 for all patients qualifying for randomization. Non-fasting blood samples (approximately 10 mL for Electrolytes, Creatinine, and Ionized Magnesium) should be collected using standard laboratory instructions and procedures provided by the laboratories.

Vital Signs

Vital signs will be measured at screening, day 1, and each subsequent office visit. Systolic and diastolic blood pressure and pulse rate over 30 seconds should be taken after patients have been at rest (seated) for at least 2 minutes. Blood pressure should be recorded in mmHg. Pulse rate should be measured in beats per minutes.

Columbia Suicide Severity Rating Scale (C-SSRS)

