- Severity of headache at the time of onset (mild, moderate, or severe) only for subjects who report a headache duration > 0)
- Acute headache pain medication(s) usage
- Study medication usage
- Unusual symptoms

Should a subject skip a day of e-diary entry, the subject will be able to provide the missing information for up to 1 calendar day. The e-diary should not be completed on the day of the office visit; the last e-diary entry for the preceding period should be completed the day prior to the office visit.

Questionnaire data required to be directly collected from subject will be obtained at each appropriate visit using an electronic device as defined in the protocol. Questionnaires are to be completed by the subject and the answers to the questions on the questionnaires should come from the subject directly, not from family, friends, or the study support personnel.

Questionnaire data required to be collected directly from clinicians will be obtained at the appropriate visit and recorded in the eCRF per protocol.

STATISTICAL ANALYSIS

Subjects will be randomized 1:1 into the treatment groups. Randomization will not include any type of stratification.

An alpha of .05 will be used for statistical significance. All statistical tests will be two-sided. All data will be analyzed using JMP (SAS Institute, Inc.).

Descriptive statistics will establish baseline characteristics and adverse event frequency. Data for the primary endpoint will be statistically analyzed via a repeated measures ANCOVA controlling for ionized serum Mg levels. Data for each of the secondary outcome measures will be statistically analyzed for both within and between group changes via a 2-tailed Repeated Measures ANOVA and/or independent or dependent t-tests as appropriate. All ANOVAs will be followed by univariate post-hoc tests as appropriate. Multiple comparison adjustments will be made if needed.

An interim analysis will be performed when approximately 60 subjects have completed the study. The results of the interim analysis may lead to stopping the study for safety or futility. The interim analysis will not lead to stopping the study for efficacy. Only the primary endpoint and first secondary endpoint of migraine and headache day reduction will be assessed at the time of the interim analysis, as well as adverse events for safety purposes.

Modified Intent-to-Treat Population (mITT)

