To compare the change from baseline of subjects treating with MLD10 versus placebo on the following parameters during a 3 month treatment period.

- migraine with aura days
- serum ionized magnesium

SAFETY ENDPOINTS

Safety assessments will include:

- adverse events

COLLECTION AND DERIVATION OF ENDPOINTS

Data required for the evaluation of endpoints will be recorded for the duration of the study using electronic data capture and included subject and clinician reported outcomes.

Following visit 2, subsequent visits will occur every 28 days for 3 months. However, in practice, there may or may not be an exact 28-day duration between 2 consecutive visits. For data analysis purposes, the number of migraine headache days during the first 28 continuous days of the run-in period will serve as the “baseline” for calculating change from baseline for 28-day periods subsequent to each office visit. If the run-in period (starting with the screening visit and preceding the day before visit 2) exceeds 28 days, the run-in period will include the last 28-days. In order to be randomized, a subject must meet 80% diary completion compliance (22 days recorded unless otherwise approved by the Sponsor and/or Clinvest).

Primary Efficacy Variable

The primary efficacy variable is the mean change from baseline in the frequency of migraine headache days per 28-day period ending with the cessation of treatment period month 3 in subjects treated with MLD10 versus placebo. This variable is derived from

the e-diary. It is based on the count of days with migraine headaches, fulfilling ICHD-3 beta criteria, and/or headaches of any duration with the use of migraine-specific acute headache medication(s). The primary time point is treatment month 3, encompassing the last 28-day period before study end.

Secondary Efficacy Variables

- Change from baseline in the frequency of headache days per 28-day period. This variable will be derived from daily e-diary reports. It will be based on the count of days with headaches.
- Change from baseline in the total cumulative hours of headache per 28-day period. This variable will be derived from daily e-diary reports. It will be based on the sum of total headache duration for days with any headache.
- Change from baseline in the average pain severity at time of onset compared to each 28-day period. This variable will be derived from the daily e-diary reports.

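### The primary ANCOVA controls for ionized serum Mg without naming a visit, so its wording admits on-treatment values that the magnesium drug may change

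*Protocol*

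**What the plan says.** The Statistical Analysis section gives the primary model in one sentence: "Data for the primary endpoint will be statistically analyzed via a repeated measures ANCOVA controlling for ionized serum Mg levels". No visit and no baseline qualifier is attached to the covariate there or elsewhere in the protocol.

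The row "Serum Ionized Mg" in Table 1 (Study Procedures) is marked at Visits 2, 3, 4 and 5 and not at Visit 1. Clinical Laboratory Tests agrees: "Blood samples will be collected for clinical laboratory testing at Visits 2-5 for all patients qualifying for randomization". Visit 2 is randomization; Visits 3, 4 and 5 close treatment months 1, 2 and 3.

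The Primary Objective is "To compare the change from baseline to treatment period months 1, 2, and 3 in the number of migraine headache days", MLD10 against placebo. Under Primary Efficacy Variable, "The primary time point is treatment month 3, encompassing the last 28-day period before study end". Exploratory Endpoints lists "serum ionized magnesium" among the parameters whose change from baseline is compared between the arms.

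The Visit 2 procedure list puts the serum draw (item 12) after dispensing of study medication (item 9). It does not say whether the draw precedes the first dose.

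**The concern.** Each of the three monthly outcomes has a matching Mg value taken at the end of the same month. In a repeated measures model, a covariate described only as Mg levels can therefore be taken as time-varying. The study drug is a magnesium salt, the rationale attributes the expected benefit to magnesium, and Mg change is compared between arms, so the protocol itself treats on-treatment Mg as something the drug may change.

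Adjusting for a variable that treatment affects has two consequences. The part of the drug effect that acts through serum Mg is taken out of the treatment coefficient. And if Mg and headache share other causes, conditioning on on-treatment Mg biases the comparison in a direction set by those causes. A value drawn before the first dose has neither problem, because randomization makes it independent of arm. The two readings are thus different models that can answer different questions, and the text does not choose between them.

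**Working it through.** **Inputs from the protocol.** Two-sided alpha 0.05, 1:1 allocation (Statistical Analysis); 80% power, and "a total sample size of 128 subjects would be needed to detect medium effects" (Power Analysis).

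**Inputs assumed, because the protocol gives none.** Shift *s* in on-treatment Mg, in within-arm Mg SDs (0.25, 0.5, 1); share *m* of the drug effect acting through Mg (0, 0.25, 0.5); Mg/outcome correlations; baseline/follow-up correlation of migraine days.

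**1. The plan's own figure.** With the stated .25 taken as Cohen's f (0.5 SD for two equal groups), a two-group ANCOVA with one covariate needs N = 128 and has 80.1% power. The planned size reproduces. Allowing 10% early termination, 128/0.9 = 142.2, against 142 in the plan. The .25 is labelled d; read literally as d it would need about 505 subjects. That is a separate matter, and 0.5 SD is used below.

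**2. On-treatment Mg, month 3 contrast.** Effects are scored as benefit and the within-arm outcome SD is held at 1, so unadjusted power is 80.1% in every cell.
- Mg slope b = 0.5m/s
- Expected estimate = 0.5(1 − m)
- SE² = (1 − b²)(1 + s²/4) × 4/N

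Worked cell, s = 1 and m = 0.5: b = 0.25; estimate 0.25; SE² = 0.9375 × 1.25 × 4/128 = 0.0366, SE 0.191; power 25.4%.

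| Mg shift | m = 0 (estimate 0.50) | m = 0.25 (estimate 0.375) | m = 0.5 (estimate 0.25) |
|---|---|---|---|
| 1 SD | 70.9% | 47.5% | 25.4% |
| 0.5 SD | 77.7% | 55.9% | 34.9% |
| 0.25 SD | 79.5% | 67.4% | not feasible (b = 1) |

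With m = 0 the estimate is unbiased and the only loss is from collinearity.

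**3. Repeated-measures check.** Simulating three months with compound symmetry (correlation 0.4 or 0.7), treatment-by-month terms and one slope for time-varying Mg gives somewhat milder losses at month 3. Power for m = 0, 0.25 and 0.5 is about 77, 54 and 28% at a 1 SD shift, and about 79, 57 and 36% at 0.5 SD.

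**4. Shared cause, no mediation, s = 0.5.** With Mg/outcome correlation ρ = 0.09 or 0.25, the estimate is 0.5 ∓ ρs and SE² = (1 − ρ²)(1 + s²/4) × 4/N.
- Cause raises Mg and lowers headache: estimate 0.455 to 0.375, power 70.1 to 55.9%.
- Cause raises both: estimate 0.545 to 0.625, power 84.6 to 94.0%.
- No drug effect: spurious difference of 0.045 to 0.125 SD, rejection 5.7 to 10.8% instead of 5%.

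**5. Visit 2 Mg instead.** The estimate stays at 0.50 SD. Power is 80.1% if Mg is unrelated to outcome and 81.7% at a correlation of 0.2. In a single-time-point simulation at s = 1, m = 0.5 (4,000 trials), the Visit 2 covariate gave estimate 0.498 and power 81%; the on-treatment covariate gave 0.248 and 25%.

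**6. Baseline migraine-day count.** With equal variance at baseline and follow-up, a change score has variance 2σ²(1 − r); adjusting for the baseline count leaves σ²(1 − r²). The ratio is (1 + r)/2.
- r = 0.7: ratio 0.85, power 86.1%
- r = 0.5: ratio 0.75, power 90.0%
- r = 0.4: ratio 0.70, power 91.8%

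This holds if the 0.5 SD effect is on the change-score scale.

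**The case against.** The strongest objection is scope. When a covariate is measured is ordinary SAP content, an unseen SAP may settle it, and no section assigns Visit 3 to 5 values to the model. The plural in the covariate's name also fits one value per subject across many subjects. What stands is that the protocol does not say on-treatment values will be used. What does not stand is that nothing needs correcting: the protocol chose to name the covariate of its primary test, and its wording can be followed literally in a way that changes what is estimated.

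A reader might infer that the primary analysis is biased, or that power will fall below 80%. The documents support neither. The Visit 2 reading is equally open, and even under the on-treatment reading power may fall, barely change (79.5% at a 0.25 SD shift with no mediation) or rise (up to 94.0% when a shared cause raises both Mg and headache).

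The sizes rest on assumptions, and the lowest powers need half the benefit to run through measured serum Mg. The protocol's own rationale warns that bioactive magnesium is hard to measure, so serum Mg may capture little of the pathway. That limits the figures to illustration.

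A reader might also take the Visit 2 sample as certainly pre-treatment. It is the only scheduled draw that can be, but the Visit 2 list leaves its order relative to dosing unstated. That objection stands and shapes the fix.

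Finally, the baseline-count covariate corrects no error. That is right; it is a recommendation for precision only.

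**Conclusion.** The point holds as an ambiguity in the stated primary model that should be closed. It is not a demonstrated bias. The covariate wording admits post-randomization Mg values, and with those the treatment coefficient may not estimate the MLD10-versus-placebo difference in the primary objective.

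The possible size ranges from negligible to serious: power of about 80% down to 25% for Mg shifts of 0.25 to 1 SD with 0 to 50% mediation, and a 6 to 11% null rejection rate with a shared cause and a 0.5 SD shift. These depend on the assumed Mg shift, mediated share and correlations, with 0.5 SD as the true effect at N = 128. Using Visit 2 Mg drawn before dosing removes the problem and leaves the planned sample size unchanged.

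**What to change.** Add after the model sentence in Statistical Analysis, in the protocol or the SAP: the ionized Mg covariate is the single Visit 2 value, from a sample drawn before the first dose; Visit 3 to 5 values do not enter the primary model and are kept for the exploratory endpoint or a labelled mediation analysis. State the pre-dose order in the Visit 2 procedures as well.

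Also add the baseline 28-day migraine-headache-day count as a covariate, for precision and not as a bias correction. It is already collected, checked for eligibility at Visit 2 (at least 3 "days of migraine during baseline") and used for the change score; the same count should serve both purposes.

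The cost is a short text change before unblinding, and preferably before the planned interim analysis, which assesses the primary endpoint for futility. No new measurements or subjects are needed, provided Visit 2 samples are in fact taken before dosing; this should be confirmed with the sites.

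### The primary model names ionized magnesium as its one covariate and omits the baseline migraine-day count, which usually costs precision and lets chance baseline imbalance into the estimate

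*Protocol*

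**What the plan says.** The Statistical Analysis section of the protocol sets the primary model in one sentence: "Data for the primary endpoint will be statistically analyzed via a repeated measures ANCOVA controlling for ionized serum Mg levels". Under Primary Efficacy Variable the outcome is a change score: "The primary efficacy variable is the mean change from baseline in the frequency of migraine headache days per 28-day period", with month 3 as the primary time point. Under Collection and Derivation of Endpoints, "the number of migraine headache days during the first 28 continuous days of the run-in period will serve as the" baseline. That count is used to form the change and to confirm eligibility at Visit 2 ("including ≥ 3 days of migraine during baseline"). Nowhere is it entered as a covariate, and the Power Analysis paragraph, which refers to an ANCOVA, names no covariate at all.

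Two further statements matter. On allocation: "Randomization will not include any type of stratification". On magnesium, under Clinical Laboratory Tests: "Blood samples will be collected for clinical laboratory testing at Visits 2-5 for all patients qualifying for randomization". The named covariate therefore exists once before treatment and three times during it, and the protocol does not say which value is meant.

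**The concern.** Subtracting the baseline count treats each extra baseline day as predicting exactly one extra day at month 3. Subjects enter partly because a noisy 28-day count met a threshold (at least 3 days, within a history of 3-14). Regression to the mean then tends to pull the true slope below 1. If it is below 1, the change score carries baseline noise that a fitted slope would remove.

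Two things are at stake. The first is power, in a trial planned at 80%. The second is the estimate itself: nothing in the design balances migraine frequency between arms, so any chance difference at baseline is only correctly removed if the slope really is 1. If an imbalance appears and the covariate is added only after unblinding, the adjustment will look post hoc. The data needed to avoid this are already collected.

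**Working it through.** **Inputs from the protocol.** Two arms, 1:1. Alpha: "An alpha of .05 will be used for statistical significance"; "All statistical tests will be two-sided". Power 80%, 128 analysed, 10% early termination, 142 randomized. The effect size is printed as d = .25.

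**Assumed inputs, because the protocol gives none.** Correlation r between the baseline and month-3 counts: 0.3-0.7. Ratio q = baseline SD / month-3 SD: 0.6-1.0. Baseline SD for the imbalance calculation: 3.3 days.

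**1. The plan's own figure.** Noncentral F with 1 numerator df, 2 groups and noncentrality f²N: f = 0.25 gives N = 128 with power 80.1%, whether the model has 0, 1 or 2 covariates. 128 / 0.9 = 142.2. So 128/142 reproduces if the printed value is read as Cohen's f = 0.25 (d = 0.5). That reading is used below.

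**2. Variance ratio, adjusted analysis over change score.**

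Ratio = (1 − r²) / (q² + 1 − 2rq), with baseline slope r/q. With equal SDs (q = 1) this reduces to (1 + r)/2. Power is at N = 128, taking f = 0.25 on the change-score SD.

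| q | r | slope | ratio | power with baseline added |
|---|---|---|---|---|
| 1.0 | 0.3 | 0.30 | 0.65 | 94% |
| 1.0 | 0.5 | 0.50 | 0.75 | 90% |
| 1.0 | 0.7 | 0.70 | 0.85 | 86% |
| 0.8 | 0.3 | 0.37 | 0.78 | 89% |
| 0.8 | 0.5 | 0.63 | 0.89 | 84% |
| 0.7 | 0.5 | 0.71 | 0.95 | 82% |
| 0.7 | 0.7 | 1.00 | 1.00 | 80% |

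In large samples the ratio never exceeds 1, and it equals 1 only when the slope is exactly 1. Restricting entry to 3-14 days tends to narrow the baseline SD, which moves q below 1. The equal-SD rows are therefore the upper end of the gain over this range of r.

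**3. Simulated counts.** Beta-binomial 28-day counts were simulated with baseline kept only if 3-14. Settings varied the assumed heterogeneity; some added month-to-month drift or 10% discontinuers given their baseline value, as the protocol's imputation rule requires. Across settings the variance ratios ran from about 0.78 to 0.97, and power from roughly 81% to 91% with baseline in the model, against about 80-84% without it. Where slopes were recorded they lay between 0.52 and 0.78. Carrying baseline forward for 10% of subjects raised the ratio by about 0.01-0.04, because those subjects have a change of zero by construction.

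**4. Baseline imbalance.** SE of the arm difference in baseline = 3.3 × √(2/71) = 0.55 day. A 2-SE imbalance is 1.1 days and arises, in one direction or the other, in about 5% of randomizations. It shifts the change-score estimate by 1.1 × (1 − slope):
- slope 0.5: 1.1 × 0.5 = 0.55 day
- slope 0.8: 1.1 × 0.2 = 0.22 day

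**The case against.** The strongest reply is that covariates belong in the statistical analysis plan, which is not at hand. The protocol sentence is a summary, does not say that magnesium is the sole covariate, and excludes nothing. Part of this stands: a later plan could add the count, and a reader who infers that the protocol rules it out goes further than the text. But the protocol does not leave the choice open. It names a covariate for the primary endpoint, and it is not the outcome's own baseline.

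A second reply is that baseline may be meant as one of the repeated measurements. The usual group-by-time contrast is then still the change-score comparison. Only a model constraining the arms to a common baseline mean would differ, and the text does not describe one.

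The third reply concerns size, and it stands. The equal-SD figures sit badly with an entry range that narrows the baseline SD, and the gain disappears at slope 1. A slope well below 1 is plausible but cannot be shown from the protocol.

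A reader might also infer that the planned test is biased or invalid, or that the sample size is wrong. Neither follows. Over repeated randomizations the change-score contrast is unbiased and type I error is held; the shift in step 4 is conditional on an observed imbalance. The 128 reproduces and does not depend on the number of covariates.

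**Conclusion.** The point holds as one of efficiency and robustness to imbalance. The primary analysis is a change score adjusted for ionized magnesium but not for baseline migraine days. The direction is firm: in large samples, adjusting for baseline cannot lose precision and usually gains it.

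The size is not firm, because the protocol gives no SD or correlation. On simulated counts the gain runs from about one percentage point of power to about ten. It is zero if the slope is 1, and the equal-SD results of 94%, 90% and 86% should be read as the upper end, not as the expected gain. The possible shift of 0.2-0.55 day rests on an assumed SD of 3.3 days, slopes of 0.5-0.8 and an imbalance seen in about one randomization in twenty.

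**What to change.** In the Statistical Analysis section, replace the model sentence with a repeated measures ANCOVA of change from baseline containing treatment, month, treatment-by-month, baseline 28-day migraine headache days and baseline-by-month, and state that the month-3 treatment contrast is primary. The covariate should be the same baseline count that is used to form the change score. If ionized magnesium is kept, restrict it to the Visit 2 value taken before the first dose, since later values can be affected by treatment and serum ionized magnesium is itself an exploratory endpoint.

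The cost is one sentence and one or a few degrees of freedom. No new data or subjects are needed, and 128/142 does not change. The change should be fixed before any unblinded look, including the planned interim analysis.
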